### 3.1.1 Screening period (Screening to randomization)

The duration of the screening period will be up to four weeks. Screening will be used to assess patient eligibility and to taper patients off prohibited medications and treatments.

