## 4.2 Exclusion criteria

Patients fulfilling any of the following criteria are not eligible for inclusion in this study. No additional exclusions may be applied by the investigator, in order to ensure that the study population will be representative of all eligible patients.

- 1. Forms of diagnosed psoriasis other than chronic plaque psoriasis (e.g., erythrodermic, generalized or localized pustular psoriasis, or new onset guttate psoriasis)
- 2. Medication-induced or medication exacerbated psoriasis (e.g., new onset or current exacerbation from beta-blockers, calcium channel inhibitors or lithium)
- 3. Previous exposure to secukinumab or any other biologic drug directly targeting IL-17A or IL-17RA receptors (e.g., ixekizumab, or brodalumab)
- 4. Diagnosis of other active ongoing skin diseases or skin infections (bacterial, fungal, or viral), or inflammatory diseases other than psoriasis that may interfere with the evaluation of psoriasis
- 5. Ongoing use of treatments prohibited by the protocol (see Section 5.5.8, Table 5-1)
- 6. Plans for administration of live vaccines during the study period or within 6 weeks before randomization
- 7. Use of any investigational treatment within 4 weeks prior to Randomization, or within a period of 5 half-lives of the investigational treatment prior to Randomization, whichever is longer

- 8. Currently enrolled in any other clinical trial involving any investigational agent or device
- 9. Patients using cholesterol-lowering medication (e.g., statins) who have not been on a stable dose for at least 90 days prior to randomization and who are unable to remain on a stable dose for the duration of the study
- 10. Pregnant or nursing (lactating) women
- 11. Women of child-bearing potential, defined as all women physiologically capable of becoming pregnant, unless they are using effective methods of contraception during dosing of study treatment and for 16 weeks after stopping of study treatment. Basic contraception methods include:
  - Total abstinence (when this is in line with the preferred and usual lifestyle of the patient. Periodic abstinence (e.g., calendar, ovulation, symptothermal, post-ovulation methods) and withdrawal are not acceptable methods of contraception

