Fasting blood glucose ≥200 mg/dL and hemoglobin A1c ≥7% at screening; fasting glucose ≥150 mg/dL up to 199 mg/dL will require consultation with the Medical Monitor to confirm eligibility

Confidential

- 16. Total white blood cell (WBC) count <2,500/μl, or thrombocytes <100,000/μl, or neutrophils <1,500/μl, or hemoglobin <8.5 g/dL at screening
- 17. Active systemic infections during 2 weeks prior to randomization (exception: the common cold) or any infection that reoccurs on a regular basis
- 18. History of an ongoing, chronic or recurrent infectious disease, or evidence of tuberculosis infection as defined by a positive or indeterminate QuantiFERON TB-Gold test (QFT) at screening.
  - NOTE: Patients with a positive QFT may participate in the study if a full tuberculosis work up (according to local practice/guidelines) completed within 12 weeks prior to randomization establishes conclusively that the patient has no evidence of active tuberculosis. If the presence of latent tuberculosis is established, then treatment must have been initiated and maintained for at least 4 weeks prior to randomization and the course of prophylaxis is planned to be completed.
- 19. Positive serology for human immunodeficiency virus (HIV), hepatitis B or C infection at screening
- 20. History of lymphoproliferative disease or any known malignancy or history of malignancy of any organ system within the past 5 years (except for skin Bowen's disease, squamous cell carcinoma, basal cell carcinoma, actinic keratoses that have been treated, carcinoma *in situ* of the cervix, or non-invasive malignant colon polyps that have been removed)
- 21. History or evidence of ongoing alcohol or drug abuse, within the last 6 months prior to randomization
- 22. History of hypersensitivity to constituents of the study treatment and/or patients who are allergic to rubber or latex (the needle cap of the single-use prefilled syringe for secukinumab and placebo may contain natural rubber latex which may cause allergic reactions in latex sensitive individuals)
- 23. Any medical, psychiatric or other condition which, in the investigator's opinion, would preclude the patient from adhering to the protocol or completing the study per protocol
- 24. Patients who are not able and/or not willing to self-administer secukinumab injections or who have no trained caregiver available to administer these injections

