## 6.4.8 Determination of tuberculosis status

Determination of tuberculosis (TB) status will be required before administration of study treatment. TB status must be determined by medical history, signs, symptoms, and TB testing (QuantiFERON-TB Gold assay). Any significant findings will be recorded in the appropriate eCRF(s), as necessary.

If the QuantiFERON-TB Gold Assay test is positive or indeterminate, a TB workup should be performed as defined by local guidelines to determine the patient's TB status.

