## 6.4.8.1 QuantiFERON TB-Gold In-Tube assay

A QuantiFERON® TB-Gold In-Tube assay will be performed to assess the TB status at screening for all patients. This test will only be used to determine patient's eligibility for the trial. The test will be used to screen the patient population for latent tuberculosis infection (Doherty, Van Vorhees and Lebwohl 2008).

This blood-based assay is specific for Mycobacterium tuberculosis and is not influenced by previous Bacillus Calmette-Guérin vaccination or exposure to other Mycobacteria species.

This test, in contrast to the purified protein derivative (PPD) skin test, is also insensitive to a booster effect since the patient is not exposed to the vaccine. The assay measures the production of interferon-gamma and presents it relative to a negative and a positive control sample (Manuel and Kumar 2008).

The QuantiFERON®-TB Gold assay test will be supplied by the central laboratory. Details on the collection, shipment of samples and reporting of results by the central laboratory are provided in the Laboratory Manual.

Confidential

The results of a TB workup for a patient with a positive or indeterminate test must be recorded in the eCRF.

- If the test result is **negative**, the patient may be randomized
- If the test result is **positive**, the investigator should perform a TB workup for the test result as per local procedures.
  - Patients **positive** for latent TB per workup may be randomized to the study if sufficient treatment has been initiated according to local routine clinical practice and will be maintained for the prescribed duration.
  - Patients **positive** for active TB per workup are not eligible for the study.
  - Patients **negative** for TB per workup (no signs of latent or active TB) may be randomized to the study.
- If the test result is **indeterminate**, it is **recommended to repeat the test once**. The investigator may decide to skip the repetition of the test and proceed directly to the workup (however this is not recommended). If a TB workup was conducted prior to screening, results from the workup can be used to assess eligibility if the workup was conducted within 12 weeks prior to randomization.
  - If the second test is negative, the patient may be randomized.

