  - If the second test is positive or indeterminate, the investigator should perform a TB workup as per local guidelines. The patient will not be eligible for randomization if: "active tuberculosis is present", or if "latent tuberculosis is present" and is untreated as per local guidelines.

Refer to Section 14 Appendix 2 to see a schematic of the tuberculosis screening process and patient eligibility with respect to TB testing.

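### Exclusion 18 and the tuberculosis procedure in 6.4.8.1 and the Appendix 2 notes disagree on indeterminate QuantiFERON results, and only Exclusion 18 sets a minimum time on latent-TB treatment

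*Protocol*

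**What the plan says.** **Protocol 4.2, criterion 18.** The list opens with "Patients fulfilling any of the following criteria are not eligible for inclusion in this study", so one criterion is enough to bar entry. Criterion 18 counts as a bar "evidence of tuberculosis infection as defined by a positive or indeterminate QuantiFERON TB-Gold test (QFT) at screening". The note that follows opens one way back: "Patients with a positive QFT may participate in the study if a full tuberculosis work up", done within 12 weeks before randomization, rules out active disease. If latent disease is found, "treatment must have been initiated and maintained for at least 4 weeks prior to randomization and the course of prophylaxis is planned to be completed". The note does not mention indeterminate results.

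**Protocol 6.4.8 and 6.4.8.1.** Section 6.4.8 treats the two results alike: "If the QuantiFERON-TB Gold Assay test is positive or indeterminate, a TB workup should be performed as defined by local guidelines". Section 6.4.8.1 recommends one repeat after an indeterminate test and allows randomization if the repeat is negative. Otherwise, "If the second test is positive or indeterminate , the investigator should perform a TB workup as per local guidelines", and the patient is then ineligible only for active disease or for latent disease left untreated by local standards. Patients with latent disease "may be randomized to the study if sufficient treatment has been initiated according to local routine clinical practice and will be maintained for the prescribed" period.

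**Protocol Appendix 2 (notes) and 3.6.3.** The notes repeat the routes of 6.4.8.1. Section 3.6.3 asks that latent disease be treated before secukinumab is given. Neither states a minimum duration.

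**SAP Table 5-1, EXCL18.** The deviation concerns active or latent tuberculosis and points to a time specified in the protocol without giving it. It does not mention indeterminate tests, and it removes patients from no analysis set.

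**The concern.** Eligibility should not depend on which section a site opens. Criterion 18 is a safety entry rule for an immunomodulating drug, and the detailed procedure meant to carry it out admits patients whom the criterion excludes. Neither text refers to the other.

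Three things are at stake:

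- **Deviation classification.** Protocol 8.1 requires full verification of adherence to the eligibility criteria, and SAP 2.3.1 tabulates and lists deviations. A patient admitted under 6.4.8.1 may be a deviation under criterion 18. EXCL18 gives no clear way to decide, and for indeterminate tests it gives none at all.
- **Monitoring.** Section 3.6.3 calls for close watch for active tuberculosis during and after treatment. Dosing runs to Week 48 in both arms, and Section 3.1.6 shows that the 52-week treatment period was still running under this amendment. It helps to know who entered with an unresolved test or with recently started prophylaxis.
- **Reporting.** The study report should be able to say which entry rule was applied.

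**Working it through.** No statistical formula applies. The check traces patient profiles through the two sets of rules.

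| Profile | Criterion 18 | 6.4.8.1 and Appendix 2 notes | Result |
|---|---|---|---|
| A. Indeterminate, then indeterminate, work-up clear | Not eligible: indeterminate excludes, and the note covers positive tests only | Not barred: neither active nor untreated latent disease | Conflict |
| B. Indeterminate, then negative repeat | Not eligible if the first result counts; eligible if the repeat does | May be randomized | Arguable |
| C. Positive, latent disease, treatment started under local practice less than 4 weeks before randomization | Not eligible | May be randomized if the treatment counts as sufficient locally | Conflict if 6.4.8.1 is followed alone |
| D. Positive, latent disease, treated 4 weeks or more, completion planned | Eligible | Eligible | Agree |
| E. Positive, timely work-up clear | Eligible | Eligible | Agree |
| F. Active disease | Not eligible | Not eligible | Agree |

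**Profile A.** The criterion names the indeterminate result as evidence of infection, and the repeat is indeterminate too. The only exception is tied to a positive test. No choice of which test counts as the screening result makes this patient eligible under 4.2, yet 6.4.8.1 describes this patient's route and does not bar entry at its end.

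**Profile B.** Criterion 18 refers to the test at screening without saying whether the first or the final result counts. If the repeat supersedes the first, the two texts agree. If not, they conflict.

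**Profile C.** Protocol 5.3 has the site confirm every inclusion and exclusion criterion before contacting the randomization system. A site that does so in full applies the 4 weeks on top of 6.4.8.1. A site that treats 6.4.8.1 as the complete tuberculosis rule finds permission to randomize, an undefined standard of sufficiency and no pointer to criterion 18.

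**The case against.** The strongest reply is that the eligibility list governs. Any one exclusion bars entry, all criteria must be confirmed before randomization, and the treatment asked for in 6.4.8.1 must be sufficient, not merely begun. On this cumulative reading, criterion 18 supplies the missing minimum and profile C is a missing cross-reference. That is a fair reading and stands as a possibility, which is why profile C is stated conditionally. The reply on profile B, that the repeat is also a screening test, is likewise reasonable. Neither helps with profile A: if criterion 18 simply governs, the work-up branch for a second indeterminate test has no effect.

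Several stronger readings are tempting but not supported:

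- **That indeterminate patients are freely admitted by 6.4.8.1.** Admission is conditional on a negative repeat, or on a work-up without active or untreated latent disease. The Appendix 2 flowchart itself is not in the text available here, so only its notes are relied on.
- **That the 4-week condition is unworkable.** The QFT is drawn at Visit 1 and "The duration of the screening period will be up to four weeks", so 28 − 28 = 0 days remain for the result and work-up when latent disease is first found at screening. But Section 6.1 allows rescreening case by case with Medical Monitor approval, and a patient already on treatment before Visit 1 can meet the condition at first screening. The tight timing is a reason for a cross-reference, not an error.
- **That the protocol gives no time for EXCL18 to refer to.** Four weeks is the only minimum duration of latent-TB treatment before randomization that the protocol states. The other sections are silent; they offer no rival figure.
- **That sites have in fact acted differently, or that these cases are common.** The documents show no such patient and give no frequency.

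It is also true that all psoriasis patients were enrolled by Amendment 2, so rewording changes no entry decision, and that judging them by a newly written rule would create deviations after the fact.

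**Conclusion.** The inconsistency is real and sits in the current text. It is unavoidable for two indeterminate tests with a clear work-up, and arguable for an indeterminate test followed by a negative repeat. For latent disease treated for less than 4 weeks, it depends on whether a site reads 6.4.8.1 together with criterion 18 or alone.

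Severity is moderate. A reader might infer that the trial's results are at risk, but EXCL18 excludes no one from any analysis set, so neither the Full Analysis Set nor the Week 12 comparison is affected. The consequences are confined to deviation classification, the account of who was eligible, and tuberculosis monitoring. The number of patients concerned cannot be estimated from the documents and may be zero.

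The conclusion rests on the wording of 4.2, 6.4.8, 6.4.8.1, the Appendix 2 notes, 3.6.3 and SAP Table 5-1. It takes no position on which tuberculosis rule is clinically right.

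**What to change.** 1. **Reconcile the protocol.** The sponsor's medical team should bring criterion 18, 6.4.8.1, Appendix 2 and 3.6.3 into one rule that covers indeterminate results (including which result counts after a repeat) and latent-TB treatment before randomization. The sections should cross-refer to each other and to rescreening in 6.1, keeping its case-by-case approval. The clinical content is for that team to decide.
2. **Align SAP EXCL18.** State the reconciled condition in place of the open reference to a protocol time, and cover indeterminate results.
3. **List affected patients.** Identify every randomized patient with an indeterminate screening QFT, or with latent tuberculosis treated before randomization for less than the 4 weeks in criterion 18. Assess them against the text in force when they entered, record which section supported admission, and check deviation status and tuberculosis monitoring.

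The cost is a protocol clarification, one SAP line and one listing. QFT results come from the central laboratory, 6.4.8.1 already requires work-up results in the eCRF for positive or indeterminate tests, and 6.4.7 captures medications from the six months before enrolment. No new procedure or data collection is needed.

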## 5 Treatment

## 5.1 Study treatment

All study treatments will be supplied by Novartis and will be labeled appropriately.

All doses of study treatment should be self-administered. Self-administration of the study treatment refers to patient self-injection or injection by a trained caregiver regardless of

whether dosing occurs at the study site or at home. Instruction and training will be provided by site staff to patients/caregivers prior to self-injection.

All doses of study treatment that are administered at the study site should be performed after all study assessments for the visit have been completed.

### 5.1.1 Study drug – secukinumab

• Secukinumab 150 mg: 1 ml liquid formulation in a single-use prefilled syringe (PFS)

Secukinumab for subcutaneous (s.c.) injection is provided in a PFS containing 150 mg secukinumab. Each secukinumab 300 mg dose is given as two s.c. injections of 150 mg.

### 5.1.2 Control drug – placebo

• Placebo to secukinumab 150 mg: 1 ml liquid formulation in a single-use prefilled syringe (PFS)

Placebo to secukinumab 150 mg for s.c. injection is provided in a matching PFS. Each PFS contains a mixture of inactive excipients, matching the composition of the secukinumab 150 mg dose. Each placebo dose is given as two s.c. injections of placebo to secukinumab 150 mg.

### 5.1.3 Additional treatment

No additional treatment beyond the study drug and control drug are included in this trial.

## 5.2 Treatment groups

At Visit 2/Baseline, eligible patients will be randomized to one of the following two treatment groups in a ratio of 2:1:

#### Secukinumab group

• Patients (or trained caregivers) will administer a dose of secukinumab 300 mg s.c. (two injections of the 150 mg PFS) once weekly for five weeks (at Baseline, Weeks 1, 2, 3, and 4), followed by dosing every four weeks, starting at Week 8 through Week 48. In order to maintain the blinding for the 12-week, placebo-controlled period, two injections of the placebo PFS will be administered at Weeks 13, 14, and 15 during the Double-blind Induction Period.

#### Placebo group

- Patients (or trained caregivers) will administer a dose of placebo s.c. (two injections of the placebo PFS) once weekly for five weeks (at Baseline, Weeks 1, 2, 3, and 4), followed by a dose after four weeks at Week 8.
- Beginning at Visit 8/Week 12, all patients in the placebo group will be switched to treatment with secukinumab 300 mg s.c. Patients will receive a dose of secukinumab 300 mg s.c. (two injections of the 150 mg PFS) once weekly for five weeks (at Weeks 12, 13, 14, 15, and 16) followed by dosing every four weeks starting at Week 20 through Week 48.

The treatment groups and dosing frequency are also described in Table 5-1 below.

Table 5-1	Overview of study treatment					
Treatment group	DB Treatment Period (Rand – Wk 12 pre-dose)	DB Induction Period (Wk 12 – Wk 15 )	OL Treatment Period (Wk 16 – Wk 52)			
Secukinumab 30	0 mg					
	2x s.c. secukinumab 150 mg injection at BSL, Wks 1, 2, 3, 4 and 8	2x s.c. secukinumab 150 mg injection at Wk 12	2x s.c. secukinumab 150 mg injection at four-week intervals			
		2x s.c. PBO injection at Wks 13, 14 and 15	from Wks 16 - 48			
Placebo (PBO)						
	2x s.c. PBO injection at BSL, Wks 1, 2, 3, 4 and 8	2x s.c. secukinumab 150 mg injection at Wks 12, 13, 14, and 15	2x s.c. secukinumab 150 mg injection at four-week intervals from Wks 16 – 48			

Confidential

DB = Double-blind; OL = Open-label; PBO = placebo; BSL = Baseline; Wk = Week

#### 5.3 Treatment assignment and randomization

At Visit 2/Baseline, all eligible patients will be randomized via Interactive Response Technology (IRT) to one of the two treatment groups. The investigator or his/her delegate will contact the IRT after confirming that the patient fulfills all the inclusion/exclusion criteria. The IRT will assign a randomization number to the patient, which will be used to link the patient to a treatment arm and will specify a unique medication number for the first package of study treatment to be dispensed to the patient. The randomization number will not be communicated to the caller.

The randomization numbers will be generated using the following procedure to ensure that treatment assignment is unbiased and concealed from patients and investigator staff. A patient randomization list will be produced by the IRT provider using a validated system that automates the random assignment of patient numbers to randomization numbers. These randomization numbers are linked to the different treatment groups, which in turn are linked to medication numbers. A separate medication list will be produced by or under the responsibility of Novartis Drug Supply Management using a validated system that automates the random assignment of medication numbers to boxes containing the study treatment.

The randomization scheme for patients will be reviewed and approved by a member of the Novartis Biometrics group.

#### 5.3.1 Stratification

Randomization will be stratified by body weight. The stratification ensures balanced allocation of patients to treatment groups within the weight strata. The strata will be "body weight < 90 kg" or "body weight  $\ge 90$  kg".

Stratification by body weight will occur at Visit 2/Baseline. The body weight collected at Visit 2 will be used for the stratification.

## 5.4 Treatment blinding

Patients, investigators/site staff, persons performing assessments, and Novartis study personnel will remain blinded to individual treatment assignment from the time of randomization until the final database lock at Week 53, using the following methods:

Confidential

- 1. Randomization data will be kept strictly confidential until the time of unblinding, and will not be accessible by anyone else involved in the study with the following exceptions:
  - specific vendors whose role in trial conduct requires their unblinding (e.g., IRT)
  - Drug Supply Management (DSM);
- 2. The identity of secukinumab and placebo prefilled syringes (PFS) will be concealed by identical packaging, labeling, schedule of administration, and appearance.

At the Week 12 primary analysis time point, there will be a database lock after all patients have completed the Week 12 visit. At that time, only the statistician and programmer(s) from the designated CRO will be unblinded in order to perform the analysis. Results from the analyses of all data through Week 12, including the data for the primary efficacy variable, will be reported. For publication purposes, summary results from the Week 12 primary analysis time point may be shared with the health care community, however individual patient-level data will remain blinded until the end of the trial.

Unblinding will only occur in the case of patient emergencies (see Section 5.5.9), at the time of the primary analysis (Week 12) for designated CRO personnel only, and at the conclusion of the study.

A full analysis of all data collected up to Week 53 will be performed when all patients have completed Follow-up Visit 1/Week 53.

